## 3 STUDY PROCEDURES

### 3.1 Subject Information and Informed Consent

The investigator or his/her representative will explain the nature of the study to the subject and answer all questions regarding this study. Prior to any study-related screening procedures being performed on the subject or any medications being discontinued by the subject in order to participate in this study, the informed consent statement will be reviewed, signed, and dated by the subject or their legally authorized representative, the person who administered the informed consent, and any other signatories according to local requirements. A signed assent should also be obtained at the same time for any adolescent subjects between 12 and 18 years of age who are participating in the study, where locally permissible and approved. A copy of the signed informed consent (and assent, if applicable) will be given to the subject, and the original will be placed in the subject's medical record. An entry must also be made in the subject's dated source documents to confirm that informed consent (and assent, if applicable) was obtained prior to any study-related procedures and that the subject received a signed copy.

Information regarding benefits for subjects and information regarding provisions for treating and/or compensating subjects who are harmed as a consequence of participation in the study can be found in the informed consent form.

Optional blood and/or skin biomarker research samples will only be collected if the subject or their legally authorized representative has voluntarily signed and dated a written consent form and assent, as applicable, describing the research. The written consent may be part of the main consent form. If the subject or their legally authorized representative does not consent to providing optional samples, the subject will still be allowed to participate in the study. A subject may withdraw consent for optional biomarker research at any time and remain in the clinical study. Data generated before subject withdrawal of consent will remain part of the study results.

Due to the COVID-19 pandemic, it is possible that additional protocol modifications not outlined in this protocol may become necessary. If this situation arises, in addition to the study informed consent, additional verbal consent may be obtained prior to these adaptations or substantial changes in study conduct in accordance with local regulations.

---

## 3.2 Medical History

A complete medical history including demographics; history of AD; previous Hepatitis B vaccination; and history of tobacco (including e-cigarettes), alcohol, and drug use will be taken at Screening. The subject's medical history will be updated at the Baseline/Study Day 0 visit, including asthma symptoms (if applicable, using the ACQ-5, see [Appendix B](#)), prior to administration of the first dose of study drug. This updated medical history will serve as the baseline for clinical assessment.

---

## 3.3 Adverse Event Assessment

Please refer to Section [4.2](#).

In the event that an enrolled subject experiences an AE related to asthma, additional information will be collected utilizing a supplemental asthma CRF.

---

## 3.4 Patient-Reported Outcomes

### Data Collection

Subjects will complete self-administered patient-reported outcome (PRO) instruments. Subjects should be instructed to follow the instructions provided with the instrument(s) and to provide the best possible response to each item. Site personnel shall not provide interpretation or assistance to subjects other than encouragement to complete the tasks. Site personnel will encourage completion of the instrument(s) at all specified visits and will ensure that a response is entered for all items.

PRO instruments that are administered at the site should be completed prior to drug administration and prior to any discussion of adverse events or any review of laboratory findings. The subject should

complete questionnaires before site personnel perform any clinical assessments and before any interaction with site personnel has occurred to avoid biasing the subject's response.

Daily Worst Pruritus NRS, daily and weekly ADerm-SS, and daily and weekly ADerm-IS ePROs will be collected from subjects electronically every evening using a handheld device provided to the subject at Screening (see Section 3.10). The handheld electronic device will be programmed to allow data entry only once per day. All data entered on the device will be immediately stored to the device itself, as well as automatically uploaded to a central server. Data from the DLQI, CDLQI, POEM, PGIS, PGIC, SCORAD (subject-reported items), and EQ-5D-5L assessments will be collected electronically at the visits specified in Section 2.1. Subjects will use a tablet device at the site to enter the required pieces of information. Starting at the Week 16 visit, Daily Worst Pruritus NRS, ADerm-SS, and ADerm-IS ePROs will also be collected electronically at the prescribed visits. The electronic tablet device will be programmed to allow data entry for only the visits specified in the protocol and will not allow subjects to complete more than one of the same assessment at any one visit. All data entered on the handheld and electronic tablet devices will be immediately stored to the devices themselves and automatically uploaded to a central server.

Data stored on the central server will be considered source. The investigator and delegated staff will be able to access uploaded subject-entered data via a password protected website until the generation, receipt, and confirmation of the study archive. Data from the ePRO system will be archived and provided to the investigator at that time as a durable record of the site's ePRO data.

### Worst Pruritus Numerical Rating Scale

The Worst Pruritus NRS (Appendix C) is an assessment tool used by subjects to report the intensity of pruritus during a 24-hour recall period. Subjects are asked to rate their pruritus at its worst during the past 24 hours on a scale of 0 to 10, with 0 being no itch and 10 being the worst imaginable itch.

### Atopic Dermatitis Symptoms Scale

The ADerm-SS (Appendix D) is an 11-item questionnaire that assesses signs and symptoms subjects may experience due to AD. The ADerm-SS includes 3 items that subjects complete daily and 8 items that subjects complete each week, both using a 24-hour recall period. The 3 daily items include worst itch during sleep hours, worst itch during waking hours, and worst skin pain. The 8 weekly items include worst skin cracking, worst pain caused by skin cracking, worst dry skin, worst skin flaking, worst rash (i.e., redness, blisters, bumpy skin), worst skin thickening, worst bleeding, and worst skin oozing. All items of the ADerm-SS are scored on an 11-point NRS ranging from 0 (no [sign/symptom concept]) to 10 (worst possible [sign/symptom concept]). The psychometric properties of the ADerm-SS are being evaluated to establish its validity in assessing AD symptoms.

## Atopic Dermatitis Impact Scale

The ADerm-IS (Appendix E) is a 10-item questionnaire that assesses a variety of impacts that subjects experience due to AD across both a 24-hour recall period (daily items 1-3) and 7-day recall period (weekly items 4-10). Items assessed daily include difficulty falling asleep, impact on sleep, and waking at night. Weekly items include household activities (e.g., washing dishes, sweeping, doing laundry), physical activities (e.g., walking, exercising), social activities, concentration, self-consciousness, embarrassment, and sadness. All items of the ADerm-IS are scored on an 11-point NRS from 0 (no impact) to 10 (extreme impact). The psychometric properties of the ADerm-IS are being evaluated to assess its validity in assessing the impact of AD to subjects.

## SCORing Atopic Dermatitis – Subject-Reported Items

The SCORAD® (Appendix F) is a validated tool used in clinical research and clinical practice that was developed to standardize the evaluation of the extent and severity of AD. The assessment consists of 3 components: A = extent or affected body surface area, B = severity, and C = subjective symptoms. Component C will be completed by subjects in this study. Subjective assessment of itch and sleeplessness is recorded for each symptom by the subject or relative on a Visual Analog Scale (VAS) on the electronic tablet, where 0 is no itch (or sleeplessness) and 10 is the worst imaginable itch (or sleeplessness), with a maximum possible score of 20.

## Dermatology Life Quality Index

The DLQI (Appendix G) is a 10-item validated questionnaire used to assess the impact of AD disease symptoms and treatment on quality of life (QoL). It consists of 10 questions evaluating impact of skin diseases on different aspects of a subject's QoL over the prior week, including symptoms and feelings, daily activities, leisure, work or school, personal relationships, and the side effects of treatment. Each item is scored on a 4-point scale (0 = not at all/not relevant; 1 = a little; 2 = a lot; and 3 = very much). Item scores are added to provide a total score, ranging from 0 to 30, with higher scores indicating greater impairment of QoL. For general inflammatory skin conditions, a change in DLQI score of at least 4 points is considered the minimum clinically important difference (MCID). In this study, the DLQI will be administered to subjects who are ≥ 16 years old at the Baseline visit.

## Children's Dermatology Life Quality Index

The CDLQI (Appendix H) is a 10-item, validated questionnaire used in clinical practice and clinical trials to assess the impact of AD disease symptoms and treatment on QoL. The CDLQI has been validated for use in subjects 4-16 years old. It consists of 10 questions assessing impact of skin diseases on different aspects of a patient's QoL over the prior week. The CDLQI items include symptoms and feelings, daily activities, leisure, school, relationships, sleep, and treatment. Each item is scored on a 4-point scale (0 = not at all; 1 = only a little; 2 = quite a lot; and 3 = very much). Item scores (0 to 3) are added to provide a total score range of 0 to 30; higher scores indicate greater impairment of QoL. In this study,

the CDLQI will be administered to subjects who are < 16 years old at the Baseline visit and will continue to be administered to these subjects for the duration of this study.

### Patient Oriented Eczema Measure

The POEM ([Appendix I](#)) is a 7-item validated questionnaire used to assess disease symptoms in both children and adults. Subjects respond to 7 items, including dryness, itching, flaking, cracking, sleep loss, bleeding, and weeping, with each item scored on a 5-point scale based on frequency (0 = no days; 1 = 1 to 2 days; 2 = 3 to 4 days; 3 = 5 to 6 days; and 4 = all days). Item scores (0 to 4) are added to provide a total score, ranging from 0 to 28, with the total score reflecting disease-related morbidity. A change in POEM score of 3.4 points is considered the MCID.

### Patient Global Impression of Severity

The PGIS ([Appendix J](#)) is a single-question assessment in which subjects describe the severity of their AD symptoms at the present moment. Subjects rate their AD symptoms on a 7-point scale, ranging from 0 (Absent, no symptoms) to 6 (Very Severe, cannot be ignored and markedly limits daily activities).

### Patient Global Impression of Change

The PGIC ([Appendix K](#)) is a single-question assessment in which subjects rate the overall change in their AD symptoms by comparing the severity of their symptoms at the present moment with the severity of their symptoms before they began study treatment. Subjects are asked to rate the overall change in their AD symptoms, with responses ranging from 1 ("Very much improved") to 7 ("Very much worse").

### EuroQoL EQ-5D-5L

The EQ-5D-5L ([Appendix L](#)) is a health state utility instrument that evaluates preference for health status (utility). The 5 items in the EQ-5D-5L comprise 5 dimensions (mobility, self-care, usual activities, pain/discomfort, and anxiety/depression) each of which are rated on 5 levels of severity. Responses to the 5 items encode a discrete health state which is mapped to a preference (utility) specific for different societies. Subjects also rate their perception of their overall health on a separate VAS.

### COVID-19 Pandemic-Related Acceptable Protocol Modifications

If electronic PRO instruments (ePROs) cannot be completed on the tablet, they are permitted to be completed via phone or video interview.

Site staff will record the subject's responses on the screen shot of the PRO in the subject's language. The date, time, and interviewer name should be recorded in the source document. The investigator or study coordinator must transcribe the PRO responses into the TrialManager website. No other site roles will receive access to enter data into TrialManager. Training will be required for investigator data entry into TrialManager and will be provided upon request of the sponsor.

If appropriate site personnel can travel to the subject's home, the ePRO tablet can be taken to the subject's home for ePRO completion. All ePROs should be completed for the assigned visit.

## 3.5 Investigator Assessments

---

Investigator assessments will be recorded on source documents and then entered into the eCRF and conducted at the study visits specified in Section 2. Assessments should be performed by the investigator or qualified site personnel. To minimize variability, the same assessor should evaluate the subject at each visit for the duration of the study. Any assessor must be competent in performing such assessments. It is the responsibility of the site primary investigator to ensure that all assessors are qualified and trained to perform assessments and that all training is documented. If the same assessor is not available, the pre-identified back-up assessor should perform such assessments.

### Eczema Area and Severity Index

The EASI ([Appendix M](#)) is a tool used to measure the extent (area) and severity of atopic eczema in 4 regions of the body (head and neck; trunk, including lower extremities; upper limbs; and lower limbs). An area score and a severity score are determined for each of the 4 regions. Each region's area score and severity score are multiplied together and then by a multiplier. The total scores from each region are added together to determine the final EASI score. Grades for dryness or scaling are not assessed by the EASI score.

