### AD Disease Activity

- ✔ 6. Diagnosis of AD with onset of symptoms at least 2 years prior to Baseline and subject meets Hanifin and Rajka criteria.
- ✔ 7. Inadequate response to treatment with topical corticosteroids (TCS) and/or topical calcineurin inhibitors (TCI), or subject for whom topical treatments are otherwise medically inadvisable (e.g., because of side effects or safety risks). Subjects are potentially eligible after appropriate washout (10 days prior to Baseline visit).
- ✔ 8. Moderate to severe AD, defined by EASI  $\geq$  16, BSA  $\geq$  10%, and a vIGA-AD score  $\geq$  3 at the Baseline Visit.
- ✔ 9. Twice-daily use of an additive-free, bland emollient for at least 7 days prior to Baseline and throughout duration of the study is required.
- ✔ 10. Baseline weekly average of daily worst pruritus NRS  $\geq$  4. (Note: The baseline weekly average of daily worst pruritus NRS will be calculated from the 7 consecutive days immediately preceding the Baseline Visit. A minimum of 4 daily scores out of the 7 days is needed.)

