## APPENDIX M. EASI SCORING EXAMPLE

An EASI score is a tool used to measure the extent (area) and severity of atopic eczema (Eczema Area and Severity Index). EASI score does not include a grade for dryness or scaling.

Assignments for the following body regions are as follows:

- Head and Neck
- Trunk: include with the lower extremities
- Upper limbs
- Lower limbs

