### **Severity Score**

Severity score is recorded for each of the four regions of the body. The severity score is the sum of the intensity scores for four signs.

The four signs are:

1. Redness (erythema, inflammation)
2. Thickness (induration, papulation, swelling – acute eczema)
3. Scratching (excoriation)

4. Lichenification (lined skin, prurigo nodules – chronic eczema)

The average intensity of each sign in each body region is assessed as: none (0), mild (1), moderate (2) and severe (3).

Score Intensity of redness, thickness/swelling, scratching, lichenification:

0 = None, absent

1 = Mild

2 = Moderate

3 = Severe

For each region, record the intensity for each of four signs and calculate the severity score.

Severity score = redness intensity + thickness intensity + scratching intensity + lichenification intensity

For each region, multiply the severity score by the area score and by a multiplier.

- Head and neck: severity score × area score × 0.1
- Trunk: severity score × area score × 0.3
- Upper limbs: severity score × area score × 0.2
- Lower limbs: severity score × area score × 0.4

Add up the total scores for each region to determine the final EASI score. The minimum EASI score is 0 and the maximum EASI score is 72.

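### The EASI instructions attach the lower extremities to the trunk and also score the lower limbs as a separate region, so a literal reading can count leg disease twice

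*Protocol*

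**What the plan says.** Operations Manual Section 3.5 (Eczema Area and Severity Index) names four regions: head and neck, then "trunk, including lower extremities; upper limbs; and lower limbs". It adds that "An area score and a severity score are determined for each of the 4 regions" and that "The total scores from each region are added together to determine the final EASI score".

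The scoring example in Operations Manual Appendix M lists the regions again. Its trunk entry reads "Trunk: include with the lower extremities", and lower limbs still have their own entry. The formula gives each region its own term, including "Head and neck: severity score × area score × 0.1", "Trunk: severity score × area score × 0.3" and "Lower limbs: severity score × area score × 0.4". Upper limbs carry 0.2, and the stated maximum is 72.

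EASI is used in several places. Protocol Section 5.1, criterion 8 begins "Moderate to severe AD, defined by EASI" and sets the threshold at 16, alongside BSA of at least 10% and vIGA-AD of at least 3. EASI 75 at Week 16 is the primary endpoint (Protocol Section 3.2, SAP Section 3.1). EASI 50 enters the Period B rescue condition. SAP Section 7.1 also plans a baseline summary of EASI by body region.

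**The concern.** The four multipliers sum to 1.0, so they work as body-region weights only if the regions do not overlap. Section 3.5 makes them overlap. An assessor who follows it literally puts leg disease into the 0.3 term and again into the 0.4 term.

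Appendix M does not settle the matter. Its trunk line can be read as putting the legs with the trunk, or as moving the trunk in with the legs. Sites could therefore diverge in more than one way.

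Three things are at stake:

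- whether a subject near the threshold of 16 is eligible;
- whether a given skin response counts as EASI 75;
- whether assessors at up to 75 sites are using the same instrument.

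**Working it through.** **Inputs from the documents.** The area bands, multipliers and maximum come from Operations Manual Appendix M. The threshold of 16 comes from Protocol Section 5.1.

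**Assumptions.** The skin findings below are illustrative. Trunk and legs are taken as equal in surface, following the rule of nines given for SCORAD in Operations Manual Appendix F (legs 2 × 18 = 36%, trunk 18 + 18 = 36%). As an alternative, the EASI multipliers would make the legs 0.4/0.7 = 57% of a merged region. Merged severity is shown undiluted and also halved by clear skin, because Appendix M asks for the average intensity within a region and does not say whether clear skin counts.

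**The plan's own figure.** Maximum severity is 12 and maximum area score is 6, so the maximum EASI is 72 × (0.1 + 0.3 + 0.2 + 0.4) = 72. This reproduces, but it does so under either reading and cannot settle the question.

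**Entry, legs only, 60% affected, severity 8.**

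- Separate regions: 4 × 8 × 0.4 = 12.8, below 16.
- Legs also in trunk: the merged region is 30% affected, area score 3. Add 3 × 8 × 0.3 = 7.2, giving 20.0.
- Merged severity halved to 4: add 3 × 4 × 0.3 = 3.6, giving 16.4.
- With a 57% leg share the merged region is 34% affected, so the area score and the 20.0 are unchanged.
- BSA does not screen this subject out: 0.60 × 36% = 21.6%, above 10%.

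**How fragile the crossing is.**

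- The 30% figure lies on the edge of a band. At 58% of the legs the separate-region score is still 12.8. The merged area is 29%, area score 2, so the total is 12.8 + 2 × 8 × 0.3 = 17.6 undiluted or 12.8 + 2 × 4 × 0.3 = 15.2 halved.
- Legs 70%, severity 6: 5 × 6 × 0.4 = 12.0 with separate regions. Adding 3 × 6 × 0.3 gives 17.4 undiluted, and adding 3 × 3 × 0.3 gives 14.7 halved.
- Legs 95%, severity 6: 6 × 6 × 0.4 = 14.4 with separate regions. The double-counted total is 19.8 (equal surface) or 21.6 (57% share), and 14.4 + 3 × 3 × 0.3 = 17.1 if halved at equal surface.

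**EASI 75, one reading throughout.** Baseline: head and neck 20%, severity 6; trunk 60%, severity 8; upper limbs 40%, severity 8; legs 60%, severity 8. The total is 1.2 + 9.6 + 4.8 + 12.8 = 28.4 under both readings, because trunk and legs are equally affected. At Week 16 the upper limbs contribute 1 × 2 × 0.2 = 0.4 and the head and neck are clear.

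- Residual disease on the legs (40%, severity 4), trunk clear. Separate: 4.8 + 0.4 = 5.2, a reduction of 81.7% (responder). Double counted: 5.2 + 2 × 4 × 0.3 = 7.6, or 73.2% (non-responder). If merged severity is halved: 5.2 + 2 × 2 × 0.3 = 6.4, or 77.5%, and status does not change.
- The same with leg severity 5. Separate: 3 × 5 × 0.4 + 0.4 = 6.4, or 77.5%. Merged severity halved to 2 or 3: 6.4 + 1.2 = 7.6 or 6.4 + 1.8 = 8.2, giving 73.2% or 71.1%. Status changes even with dilution.
- Residual disease on the trunk (60%, severity 6), legs clear. Separate: 7.2 + 0.4 = 7.6, or 73.2% (non-responder). Merged: 5.8 (equal surface) or 4.0 (57% share), giving 79.6% or 85.9% (responder).

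**EASI 75, reading changed between visits.** Baseline is legs 60%, severity 8. Week 16 is legs 35%, severity 4, so 3 × 4 × 0.4 = 4.8 with separate regions.

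- Separate at both visits: 1 − 4.8/12.8 = 62.5%.
- Double counted at both visits: Week 16 is 4.8 + 2 × 4 × 0.3 = 7.2, and 1 − 7.2/20.0 = 64%.
- Double counted at Baseline only: 1 − 4.8/20.0 = 76%.

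**The case against.** The strongest reply is that the formula in Appendix M is clear. It has four terms, lower limbs stand alone, and the multipliers sum to 1.0. Operations Manual Section 3.5 also requires trained assessors, the same assessor at each visit where possible, and a pre-identified back-up. A trained assessor may well score four separate regions whatever the text says. Training material and eCRF pages are not among the documents, so actual scoring cannot be judged. That stands, and it limits the claim to what the wording permits. It does not correct the wording: the Operations Manual is the scoring reference supplied to sites, and training is each site investigator's responsibility.

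Four further points stand.

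- Appendix M is ambiguous, not a clean repeat of Section 3.5.
- The entry examples assume eczema on the legs alone, and the documents do not show how common that is. Where the trunk is worse than the legs, merging can lower the score. Where they are equal, it changes nothing.
- Some of the crossings disappear if severity is diluted by clear skin, as shown above.
- A reader might infer from the 76% figure that double counting by itself turns a non-responder into a responder. In that example it does not: used at both visits it gives 64%, the same status as 62.5%. The change comes from switching readings within one subject, which the same-assessor rule makes less likely but does not exclude.

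**Conclusion.** The inconsistency is certain and sits in the scoring reference for the primary endpoint. Its effect on the data is possible but not shown.

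On the stated assumptions, leg-only disease at 60% and severity 8 moves from 12.8 to between 16.4 and 20.0, across the entry threshold. EASI 75 status can move either way when trunk and legs respond differently, or when different readings are used at different visits. One changed subject is worth 1/31 = 3.2 percentage points in the placebo arm and 1/62 = 1.6 points in a risankizumab arm.

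A reader might infer that trial scores were in fact inflated, or that the comparison is biased towards one arm. The documents support neither. They do not show which reading sites used, and the wording is identical in all arms under blinded assessment. The risks are misclassified eligibility, measurement noise and inconsistency between sites. The sample-size calculation does not depend on this point: 15% versus 51%, with 31 and 62 subjects at two-sided 0.025, gives 90.7% power by the pooled normal approximation, consistent with the stated figure.

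**What to change.** In Operations Manual Section 3.5, remove the words attaching the lower extremities to the trunk. In the region list of Appendix M, remove the same attachment from the trunk line. Add one sentence saying that each body area is scored in exactly one of four non-overlapping regions, matching the multipliers 0.1, 0.3, 0.2 and 0.4. Check that assessor training and the eCRF agree.

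Before the Week 16 database lock, ask each site which reading its assessors used. Do not try to infer this from recorded trunk scores, because an area score of 0 to 6 cannot show whether the legs were included. For subjects already enrolled, record the reading used at Baseline and score Week 16 the same way. Otherwise the correction itself could cause the within-subject switch shown above.

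The cost is two short deletions, one added sentence, a site memo with one question, and a check of training and eCRF pages. No new visits or procedures are needed.
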